7.3.1 Baseline data

After enrollment (see Chapter 10 for the recruitment and consent procedure), a preoperative baseline evaluation will be performed and the following data will be collected (CRF A):

- Month and year of birth
- Gender
- Smoking
- Pre-operative diagnosis
- Prior treatment to affected spinal levels
- Concurrent medical conditions
- ASA classification
- Disease related medication use (including NSAID use)
- Questionnaires
 - EQ-5D-5L
 - ODI
- VAS pain score
 - Back pain related to diagnosis
 - Leg pain related to diagnosis
 - Pain in left iliac crest
 - Pain in right iliac crest
 - Pain drawing

The EQ-5D-5L is a standardized instrument for use as a measure of health outcome. Applicable to a wide range of health conditions and treatments, it provides a simple descriptive profile and a single index value for health status that can be used in the clinical and economic evaluation of health care as well as population health surveys. The Oswestry Low Back Pain Disability Index (ODI) is an evaluation questionnaire related to patient perception of the effect of his/her current low back pain on activities of daily living. A Visual Analogue Scale (VAS) will be used to record back pain, leg pain and iliac crest pain at the left and right side at all evaluation points. As a supplement, patients will be asked to make a pain drawing to get a graphic representation of the pain and its physical distribution.

7.3.2 Surgical and postoperative procedures

Patients will be operated according to standard surgical procedures for instrumented posterolateral fusions between T10 and S2, with the only exception that one side of the spine will be grafted with the synthetic ceramic material MagnetOs™ Granules instead of bone harvested from the iliac crest. A recommended surgical technique is provided in Appendix B. In advance, the participating orthopaedic surgeons of each center will receive instructions on appropriate use of MagnetOs™ Granules from the principal investigator. Any questions that may arise concerning the surgical aspects of using MagnetOs™ Granules or autograft will be answered by the principal investigator.

Standard prophylactic antibiotics will be given for at least 24 hours, according the local surgical guidelines of each center. A thrombosis prophylaxis will be used according to the surgeons' preference. If preferred by the surgeon, patients will receive a restraining brace or orthosis postoperatively in order to protect the spine from (excessive) movements. Mobilization will be encouraged on the first postoperative day; physiotherapy will be offered during hospitalization and ambulatory if indicated.

According to standard care, standing anteroposterior and lateral radiographs will be taken postoperatively during hospitalization.

During surgery and hospital admission, the following information will be collected (CRF B):

- Date of surgery
- Surgeon's name
- Surgical technique
 - Instrumented spinal levels
 - Levels of decompression
 - Performance of vertebral osteotomy
 - Use of interbody device
 - Insertion side of TLIF
 - Additional surgical procedures
- With the use of a 20ml syringe an estimation of the volumes (in mL) of:
 - 1) obtained local bone and 2) obtained iliac crest bone and 3) the ratio of local bone / iliac crest bone used for posterolateral fusion
 - Local bone (or mixed autograft) applied per level for interbody fusion
 - (Mixed) autograft used per posterolateral fusion level

- Estimation of volume of MagnetOsTM Granules per posterolateral fusion level (in cc)
- Iliac crest side used for bone harvesting (right/left)
- Iliac bone harvested via same incision (yes/no)
- Additional time required for bone graft harvesting (minutes)
- Allocation of MagnetOsTM Granules (left/right)
- Surgical time (skin to skin and total anaesthesia time (begin and end of sedation)
- Estimated blood loss (cc)
- Use of vancomycine powder
- Intra-operative complications
- Postoperative X-rays
- Date of discharge
- Disease related medication use (including NSAID use)

7.3.3 Planned follow-up moments

The subsequent follow-up moments will take place at the outpatient clinic and are based on the standard care at the UMC Utrecht. The data described below will be collected at 6 weeks, 3 months, 1 year and 2 years postoperatively. The questionnaires, CT-scan at 2 years follow-up in case of no or doubtful fusion at 1 year follow-up, and depending on the local follow-up protocol the CT-scan at one year follow-up and/or X-ray at two years follow-up, are extra for this study. In addition to the baseline questionnaires, treatment satisfaction will be assessed with a Numeric Rating Scale (NRS).

6 weeks (±14 days; CRF C)

- Complications / (serious) adverse events
- Disease related medication use (including NSAID use)
- Questionnaires
 - EQ-5D-5L
 - ODI
 - NRS satisfaction
- VAS pain score
 - Back pain related to diagnosis
 - Leg pain related to diagnosis
 - Pain in left iliac crest

- Pain in right iliac crest
- Pain drawing
- Imaging
 - Standing anteroposterior and lateral radiographs
- Radiologic evaluation by treating surgeon (indications for failure or deformation / instability)

3 months (\pm 21 days; CRF D)

- Complications / (serious) adverse events
- Disease related medication use (including NSAID use)
- Questionnaires
 - EQ-5D-5L
 - ODI
 - NRS satisfaction
- VAS pain score
 - Back pain related to diagnosis
 - Leg pain related to diagnosis
 - Pain in left iliac crest
 - Pain in right iliac crest
 - Pain drawing
- Imaging
 - Standing anteroposterior and lateral radiographs
- Radiologic evaluation by treating surgeon (indications for failure or deformation / instability)

1 year (12-15 months; CRF F)

- Complications / (serious) adverse events
- Disease related medication use (including NSAID use)
- Questionnaires
 - EQ-5D-5L
 - ODI
 - NRS satisfaction
- VAS pain score
 - Back pain related to diagnosis
 - Leg pain related to diagnosis
 - Pain in left iliac crest

- Pain in right iliac crest
- Pain drawing
- Imaging
 - Standing anteroposterior and lateral radiographs
 - CT-scan
- Radiologic evaluation by treating surgeon (indications for failure or deformation / instability)
- Fusion assessment based on CT-scan by treating surgeon per level and per side in three planes, without the distinction between graft-related or non-graft-related fusion as described in Appendix C.

2 years (22-26 months; CRF G)

- Complications / (serious) adverse events
- Disease related medication use (including NSAID use)
- Questionnaires
 - EQ-5D-5L
 - ODI
 - NRS satisfaction
- VAS pain score
 - Back pain related to diagnosis
 - Leg pain related to diagnosis
 - Pain in left iliac crest
 - Pain in right iliac crest
 - Pain drawing
- Imaging
 - Standing anteroposterior and lateral radiographs
 - CT-scan of all patients with a doubtful fusion or non-union after 1 year, as assessed by the blinded observer
- Radiologic evaluation by treating surgeon (indications for failure or deformation / instability)
- Fusion assessment based on CT-scan by treating surgeon per level and per side in three planes, without the distinction between graft-related or non-graft-related fusion as described in Appendix C.

7.4 Radiologic evaluation

7.4.1 X-rays

The regular standing anteroposterior and lateral radiographs will be evaluated locally by the treating surgeon. Indications for failure like material breakage or loosening and deformation or instability like osteolysis will be recorded, as well as indications for bone bridging.

7.4.2 CT-scans

The CT-scans will be reviewed both locally by the treating surgeon and centrally by an assessment panel consisting of at least one spine surgeon and an uninvolved specialist. This panel will be blinded to the treatment allocation and perform the assessments independently on de-identified CT-scans (see Appendix C).

Each instrumented spinal level, that is not part of an osteotomized segment, will be unilaterally assessed for posterolateral fusion according the protocol, based on literature³⁵⁻³⁷ and experience from the AxA study. This grading system consists of three categories:

1. “Fusion” is defined as a continuous bony bridge from one vertebra to the other, in absence of any secondary signs of nonunion, such as fracture or loosening of the screws or rods (= 2 points);
2. “Doubtful fusion” indicates doubts about continuity or quality of the bony bridge (= 1 point);
3. “No fusion” indicates definite discontinuity or lack of the fusion mass, as well as obvious indications of mobility like material failure or apparent pseuocoarthrosis (= 0 points).

Assessemnt of posterolateral fusion is scored in the coronal, sagittal and axial plane. A segment will be regarded fused if at least one plane shows definite fusion (2 points) and at least one other plane a doubtful fusion (at least 1 point). Interbody fusion will be assessed in two planes and scored similarly.

The final assessment panel will score two locations of posterolateral fusion separately: between the transverse process and >1mm lateral or above the rod (graft related) and directly around the rod or fusion of the facet joint (probably not graft related). See Appendix C for a more detailed description of the CT-assessment for the primary and secondary outcomes.

The CT-scans will also be evaluated for the volume of fusion bone, signs of heterotopic ossification (i.e. extension of fusion mass beyond the intended fusion level) and if possible, the presence of graft remnants will be recorded.

7.5 Withdrawal of individual patients

Patients can leave the study at any time for any reason if they wish to do so without any consequences. The investigators can decide to withdraw a patient from the study for urgent medical reasons. In case an intra-operative decision is made to perform something different than what was intended for study enrollment like for example to use local bone graft only or an uninstrumented spinal fusion, the patient will be considered a per-operative withdrawal and will not be treated with MagnetOs™ Granules. Protocol violations where the (surgical) procedure or follow-up (e.g. timing of one-year CT-scan) will influence the primary outcome will be regarded individually and may lead to withdrawal.

7.6 Replacement of individual subjects after withdrawal

Per-operative withdrawals will be replaced. Patients who are withdrawn or lost to follow-up post-operatively, i.e. after the treatment with MagnetOs™ Granules, will not be replaced in this study, unless the anticipated drop-out rate of 15% is exceeded.

7.7 Follow-up of subjects after withdrawal

All data collected until withdrawal will be used for the analyses as described in the protocol, unless the patient made an explicit objection. All withdrawn patients will be followed according to standard care.

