7. METHODS

7.1 Study outcomes

7.1.1 Primary study outcomes

1. Posterolateral spinal fusion rate at one-year follow-up (assessed on CT-scans);
2. Rate of (serious) adverse events that are related to the procedure in any way, and their potential relation with MagnetOsTM Granules.

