7.8 Failures

Patients that need revision surgery that influences the fusion, will be considered failures and only excluded from the primary analysis and secondary outcomes related to the performance of MagnetOs™ Granules. This because the treatment effect on one side of the spine cannot be distinguished from the effect on the other side, so intention to treat analyses are not possible. Patients registered as failure will not be replaced, as the total number of patients takes this into account. Follow-up will continue according to the study protocol.

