8.2 AEs and SAEs

8.2.1 Adverse events (AEs)

Adverse events are defined as any undesirable medical experience occurring to a subject during the study, whether or not considered related to MagnetOsTM Granules. All adverse events that can be related to the surgical procedure that are observed by the participating investigators or their staff, or reported by the subject between or at the follow up visits, will be recorded in the Case Report Form. An overview and analysis of all these adverse events will be included in the final study report. AEs that are related to previous known or unknown diseases, or conditions that cannot be related to the procedure (like accidents or other interventions), will not be recorded.

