9.2 Primary safety analysis

(Serious) adverse events occurring during the study that may in any way be related to the surgical procedure will be reported in adverse event tables. The frequency and nature of events will be compared to events in control populations from literature.

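### Section 7.7 makes no provision for recording new adverse events in implanted patients whom the investigators withdraw, so the primary safety rate can be understated

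*Combined protocol and SAP*

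**What the plan says.** Section 7.5 gives two grounds on which an investigator can take an implanted patient out of the study. The first is medical: "The investigators can decide to withdraw a patient from the study for urgent medical reasons". The reasons are not defined further. The second is a protocol violation that affects the primary outcome, with one-year CT timing as an example; such cases "will be regarded individually and may lead to withdrawal". Section 7.6 confirms that withdrawal after treatment with MagnetOs is foreseen.

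Section 7.7 sets the consequence: "All data collected until withdrawal will be used for the analyses as described in the protocol", unless the patient objects, and then "All withdrawn patients will be followed according to standard care".

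Section 7.8 has a separate rule for failures, meaning patients whose revision surgery influences the fusion. They leave only the primary analysis and the secondary outcomes on graft performance, and "Follow-up will continue according to the study protocol".

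On safety, section 7.1.1 lists as the second primary outcome "Rate of (serious) adverse events that are related to the procedure in any way". Section 8.2.1 defines an AE as "any undesirable medical experience occurring to a subject during the study". Section 9.2 states how the outcome is judged: "The frequency and nature of events will be compared to events in control populations from literature".

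**The concern.** Withdrawal by an investigator does not end exposure. The graft is placed once, at surgery, and stays in the patient (section 6.2 tests it as a permanent implant, while also describing it as resorbable). What withdrawal ends is protocol follow-up. For a fusion endpoint that can be defended, since a patient with a mistimed scan cannot be scored as planned. For a safety endpoint the patient is still fully informative, and nothing in the plan says that new events will still be recorded.

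Three features make this matter here:

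- Every patient receives both grafts, and the safety comparison is with published populations. No concurrent arm shares the same loss, so an undercount is not offset. With all implanted patients in the denominator, missed events can only move the rate in the favourable direction.
- Section 6.3 states that the product has not been studied clinically before, and section 6.4 lists long-term risks.
- Secondary outcome 5, long-term complications (section 7.1.2), has the same gap.

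**Working it through.** **1. The plan's own figure.** The documents give no sample size, margin or expected rate for safety. The only figure to reproduce is the efficacy sample size (section 4.4 and Appendix A): discordance 0.30, margin 0.15, one-sided alpha 0.05, power 80%.

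- Normal approximation: N = 0.30 × (1.6449 + 0.8416)² / 0.15² = 82.4, so 83.
- Exact power of the restricted-maximum-likelihood score test at N = 84: 0.80098, equal to the Appendix A row.
- Allowance for 15% non-evaluable: 84 / 0.85 = 98.8, so 99, consistent with 100 enrolled.

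The efficacy size is sound and this point does not touch it.

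**2. The rules side by side.**

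| Group | Received MagnetOs | Study data | Follow-up |
|---|---|---|---|
| Per-operative withdrawal (7.5, 7.6) | No; replaced | – | Standard care |
| Failure after revision (7.8) | Yes | Continue; only fusion-related analyses exclude the patient | Study protocol |
| Withdrawn by investigator after surgery (7.5, 7.7) | Yes | Up to withdrawal | Standard care |

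Only the third row is at issue.

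**3. Could a new event after withdrawal still be recorded?**

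- Sections 8.2.1 and 8.2.2 record procedure-related events that study staff observe, or that the subject reports at or between follow-up visits. Neither mentions withdrawn patients.
- Section 8.3 follows AEs already reported until they resolve, stabilise or the last study visit arrives. It does not cover new ones.
- Section 7.3.3 bases the visits on standard care at the coordinating centre, so clinical contact probably continues. The Summary describes only the first year in those terms, and the two-year X-ray may be extra, depending on the site.
- Under section 11.1 the coordinating team receives CRFs, images, (S)AE forms and relevant additional information, not source records. An event noted only in the hospital record does not reach the analysis unless someone at the site enters it.

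The plan therefore neither provides for such recording nor forbids it.

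**4. Length of the gap.** For the one follow-up violation that section 7.5 names, the CT window closes at 15 months and the last visit falls at 22-26 months. Withdrawal at 15 months leaves 22 − 15 = 7 to 26 − 15 = 11 months uncovered. Withdrawal for urgent medical reasons can come at any time, so its gap cannot be stated.

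**5. Illustration of size (all inputs assumed).** Let p be the true per-patient event rate, w the share withdrawn, k the withdrawn patients' risk relative to the overall rate, and f the share of their events that is missed. Then

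observed rate = p − w × k × p × f.

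With w = 5% and f = 1:

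| True rate p | k = 1 | k = 2 | k = 3 |
|---|---|---|---|
| 10% | 9.5% | 9.0% | 8.5% |
| 20% | 19% | 18% | 17% |
| 30% | 28.5% | 27% | 25.5% |

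For example, 0.20 − 0.05 × 3 × 0.20 × 1 = 0.17. If half the events are missed (f = 0.5), each loss halves and a true 20% reads 19.5%, 19% or 18.5%. With 100 implanted, one withdrawn patient can lower the per-patient rate by at most 1 percentage point.

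As an extreme bound, if all 15% non-evaluable patients were such withdrawals, a true 20% would read 17%, 14% or 11%. That bound is not realistic: section 4.4 counts revisions, deep infections, loss to follow-up and poor scans in the 15%.

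**The case against.** The strongest reply is that the gap is narrow and the text is silent rather than prohibitive. Most of this stands, and it rules out several stronger readings that a reader might infer.

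- *The patients most likely to have events are the ones lost.* Not shown. The clearest high-event group, patients with revision surgery, stays on protocol follow-up (7.8). The event that prompts a withdrawal is kept, because data up to that point are used, and section 8.3 follows AEs already reported.
- *Sections 7.7 and 7.8 contradict each other.* They do not. One covers withdrawn patients and the other covers failures, who are not withdrawn. Section 7.8 shows only that the plan can already separate evaluability for fusion from safety follow-up.
- *Later events have no route into the CRF or the SAE report.* Too strong. Events observed by site staff may be recorded. Section 11.5 ends the study at the last patient's last visit, so being in the study need not stop at one patient's withdrawal.
- *The safety halt is starved of information.* Section 8.1 suspends the study on sufficient grounds of danger to subjects and does not tie this to reported events.
- *The undercount is 10-20%.* This needs 5-10 investigator withdrawals with a 30% later-event risk (1.5-3 events) set against 15 true events. None of these inputs is in the documents. The 10-13 per 100 left after taking 2-5% revisions and deep infections from 15% also mixes in loss to follow-up and poor scans.

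What the reply does not remove is that section 7.7, read as written, stops the use of study data at withdrawal, and that standard care supplies contact but not study recording.

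**Conclusion.** The point holds in a limited form. Under the stated rule, new procedure-related AEs and SAEs in an implanted patient can go unrecorded once an investigator withdraws that patient, even when the reason has nothing to do with safety, such as a mistimed CT. Because the rate is a primary outcome set against literature controls, any such loss favours the product. Loss is possible, not certain.

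The size cannot be estimated from the documents. The 17-19% reading of a true 20% rests on four assumptions: a per-patient rate with all implanted patients in the denominator, 5% withdrawn, one to three times the overall risk, and all of their events falling after withdrawal and being missed. Fewer withdrawals or partial capture through standard care would make the loss smaller.

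**What to change.** Amend section 7.7 so that a patient who received MagnetOs and is withdrawn by the investigator leaves only the fusion analyses, as section 7.8 already arranges for failures. State that AE and SAE collection continues to the two-year visit unless the patient objects. In section 9.2, define the safety population as all implanted patients, and report withdrawals by reason and by time since surgery.

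The cost is a short amendment and a few extra CRF pages. No study procedure is added and the sample size does not change. The information letter and consent form (section 10.2, documents E1 and E2) are not among the documents reviewed, so their wording on data after withdrawal should be checked and may or may not need a line added.

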7.8 Failures

Patients that need revision surgery that influences the fusion, will be considered failures and only excluded from the primary analysis and secondary outcomes related to the performance of MagnetOs™ Granules. This because the treatment effect on one side of the spine cannot be distinguished from the effect on the other side, so intention to treat analyses are not possible. Patients registered as failure will not be replaced, as the total number of patients takes this into account. Follow-up will continue according to the study protocol.

7.9 Premature termination of the study

All (serious) adverse advents that can be related to the surgical procedure in any way will be reported to the principal investigator as described in Chapter 8 and evaluated. If a relation to the performance of MagnetOsTM Granules is suspected, the allocation side can be disclosed. These findings will be discussed with the METC.

8. SAFETY REPORTING

8.1 Temporary halt for reasons of subject safety

In accordance to section 10, subsection 4, of the WMO, the sponsor will suspend the study if there is sufficient ground that continuation of the study will jeopardise subject health or safety. The sponsor will notify the accredited METC without undue delay of a temporary halt including the reason for such an action. The study will be suspended pending a further positive decision by the accredited METC. The investigator will take care that all subjects are kept informed.

8.2 AEs and SAEs

8.2.1 Adverse events (AEs)

Adverse events are defined as any undesirable medical experience occurring to a subject during the study, whether or not considered related to MagnetOsTM Granules. All adverse events that can be related to the surgical procedure that are observed by the participating investigators or their staff, or reported by the subject between or at the follow up visits, will be recorded in the Case Report Form. An overview and analysis of all these adverse events will be included in the final study report. AEs that are related to previous known or unknown diseases, or conditions that cannot be related to the procedure (like accidents or other interventions), will not be recorded.

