2. OBJECTIVES

2.1 Primary objectives

The primary objective of this study is to demonstrate the non-inferiority of MagnetOsTM Granules as compared to autologous bone graft in instrumented posterolateral fusion of the thoracolumbar and lumbosacral spine, in terms of efficacy and safety.

1. Efficacy will be based on the posterolateral spinal fusion rate assessed at one-year CT-scans;
2. Safety will be evaluated by documenting the number and nature of all (serious) adverse events that may in any way be related to the surgical procedure. The complication rate will be compared to the rate in control populations from literature.

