Although iliac crest donor site morbidity is often reported by patients, the relevance of donor site pain is disputable when the bone is harvested via the same incision as used for the spinal fusion.³ The preliminary results of the AxA study indeed indicate that there is no relation between the real donor site and the iliac crest that is indicated by blinded patients. To determine if the often reported high incidence of donor site pain can be explained by the knowledge of the patient where the bone graft was taken, we will not blind the patients for the donor site in this study. The outcomes measures reported by patients unblinded to the iliac crest donor site will be compared to the outcomes of the blinded patients from the AxA study.

5. Combine the study populations of the current study and the AxA study

To combine the study data of both the current study and the AxA study will allow investigations on more infrequent phenomena on a relatively large population. Such a phenomenon is for example adjacent segment disease. This is a longterm complication where the adjacent joints and intervertebral disc may wear faster and cause degenerative disease. The occurrence of adjacent segment disease may be related to length of the construct and restoration of the sagittal balance. The occurrence of typical complications like infection and pseudoarthrosis can be related to risk factors like comorbidities, smoking, length of instrumented segment and so on.

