6.3 Summary of findings from clinical studies

No clinical investigations of MagnetOsTM Granules have been performed to-date.

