8.2.2 Serious adverse events (SAEs)

A serious adverse event is any untoward medical occurrence or effect that:

- Results in death;
- Is life threatening (at the time of the event);
- Requires hospitalization or prolongation of existing inpatients' hospitalization;
- Results in persistent or significant disability or incapacity;
- Is a congenital anomaly or birth defect; or
- Any other important medical event that did not result in any of the outcomes listed above due to medical or surgical intervention but could have been based upon appropriate judgement by the investigator.

An elective hospital admission for other reasons will not be considered as a serious adverse event.

All SAEs that can be related to the surgical procedure that are observed by the local principal investigators or their staff, or reported by the subject between or at the follow up visits, will be recorded in the Case Report Form. The investigator will report all these SAEs to the sponsor within 24 hours after obtaining knowledge of the events by sending the SAE form. SAEs that are related to a previous known or unknown disease, or conditions that cannot be related to the procedure (like accidents or related to other interventions) will not be recorded.

The sponsor will report all reported serious adverse events through the web portal *ToetsingOnline* to the accredited METC that approved the protocol, within 7 days of first knowledge for SAEs that result in death or are life threatening followed by a period of maximum of 8 days to complete the initial preliminary report. All other SAEs will be reported within a period of maximum 15 days after the sponsor has first knowledge of the serious adverse events.

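### The AE and SAE recording rules conflict for events with both a disease and a possible surgical cause, so part of the primary safety outcome may go unrecorded

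*Combined protocol and SAP*

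**What the plan says.** Section 8.2.1 of the protocol defines an adverse event broadly, as "any undesirable medical experience occurring to a subject during the study", "whether or not considered related to MagnetOsTM Granules". Two recording rules follow.

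- **Include.** "All adverse events that can be related to the surgical procedure" are entered in the CRF when staff observe them or the patient reports them.
- **Exclude.** "AEs that are related to previous known or unknown diseases, or conditions that cannot be related to the procedure" are not recorded. Accidents and other interventions are given in brackets as examples.

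Section 8.2.2 repeats the pair for serious events. Those that can be related to the operation are recorded and sent to the sponsor within 24 hours, while "SAEs that are related to a previous known or unknown disease, or conditions that cannot be related to the procedure" are left out.

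The primary safety objective (section 2.1) and outcome (section 7.1.1, item 2) cover events with any kind of relation to the operation. The outcome adds their possible relation to MagnetOs. The only comparator is external: "The complication rate will be compared to the rate in control populations from literature". Section 9.2 says the same and gives no rate, margin or test.

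**The concern.** The exclusion names two things: diseases, previous or unknown, and conditions that cannot be related to the procedure. If the final clause limits only the second, the disease class stands alone. A wound infection in a patient with diabetes is then related to surgery and also to a previous disease. One sentence says to record it, the other says not to.

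The exclusion uses causality to decide whether a record exists, instead of recording causality as an assessment. That matters here for three reasons.

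- Every patient receives both grafts, so there is no concurrent safety arm. Under-recording cannot cancel between groups. It goes straight into the absolute rate that is compared with the literature.
- Section 6.3 states: "No clinical investigations of MagnetOsTM Granules have been performed to-date". Experience for judging which events the product may cause is therefore limited. The exclusion is framed on disease and procedure and does not mention the product.
- Later safety steps work on what was recorded: evaluation by the principal investigator (7.9), the suspension decision (8.1), SAE reports to the ethics committee (8.2.2) and the annual report (11.4).

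**Working it through.** The plan states no adverse event rate, comparator rate, safety margin or safety power, so there is no safety figure to reproduce. The check is a comparison of the passages, followed by an illustration.

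**Step 1. How each type of event is treated**

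| Event | Include rule (8.2.1, 8.2.2) | Exclude rule, literal reading | In the primary safety outcome (2.1, 7.1.1)? |
|---|---|---|---|
| Surgical cause only | record | does not apply | yes |
| Disease cause only | does not apply | do not record | no |
| Disease and possible surgical cause | record | do not record | yes |
| Surgical event that the site wrongly attributes to a disease | record, if seen as possibly surgical | do not record | yes |

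The first two rows are consistent. The third is a direct conflict. The fourth leaves no trace by which the error could be found.

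**Step 2. Whether the sentence can be read otherwise.** It can. If the clause about not being relatable to the procedure limits diseases as well as conditions, the exclusion is the complement of the include rule and the conflict disappears. The bracketed examples, accidents and other interventions, illustrate conditions rather than diseases, which favours the literal reading but does not settle it. No precedence is stated.

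**Step 3. What can be seen centrally.** Under 8.2.2 only the recorded SAEs go to the sponsor. Under 11.1 the central investigators receive completed CRFs, images, (S)AE forms and relevant additional information, but have no access to source data. An event excluded at the site appears on none of these forms.

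**Step 4. Direction and illustrative size.** Let *f* be the share of procedure-related events that sites attribute to a disease and leave out. Then

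recorded rate = true rate × (1 − *f*).

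Both inputs are assumptions, because the documents give neither.

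| Assumed true rate | *f* = 0 | *f* = 10% | *f* = 25% | *f* = 50% |
|---|---|---|---|---|
| 5% | 5% | 4.5% | 3.75% | 2.5% |
| 20% | 20% | 18% | 15% | 10% |
| 40% | 40% | 36% | 30% | 20% |

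For example, 20% × (1 − 0.25) = 15%, or 5 events lost per 100. The rate falls whenever *f* is above zero. The value of *f* is unknown.

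**The case against.** The best defence is that the protocol is inclusive wherever it describes the purpose of safety data. Sections 2.1, 3, 7.1.1, 7.9, 8.2 and 9.2 all refer to events that can be, or in some way may be, related to the operation. A site that follows them loses nothing. Restricting the outcome to procedure-related events is a declared design choice, and a broad AE definition with a narrower recording rule is not in itself a contradiction. Monitors can see source data (11.1) and check completeness (11.2). The product is CE-marked and cleared in the US (6.1), and the study is classed as negligible risk (11.2).

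Most of this stands, and it limits the point to events of mixed or mistaken cause. It does not remove the point, because the exclusion is a written instruction and a site that applies it literally is following the protocol. For the same reason, a monitor has no clear discrepancy to query when such an event is missing.

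Two stronger readings are tempting, and the documents do not support them.

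- *A reader might infer that sites discard every disease-linked event and that the safety rate is therefore too low.* Events due only to disease lie outside the outcome by design, so leaving them out does not bias it. For mixed-cause events the loss is a risk, not an established effect.
- *A reader might infer that secondary objective 5 loses the comorbidity-related events it needs.* Section 2.3 says that "typical complications like infection and pseudoarthrosis can be related to risk factors like comorbidities, smoking, length of instrumented segment". Comorbidity is thus an explanatory variable there, collected at baseline (7.3.1). Infection and pseudoarthrosis are treated as typical complications, which the include rule covers. Pseudoarthrosis is also scored on CT (Appendix C), and revisions that influence the fusion are registered as failures (7.8). Adjacent segment disease is studied against construct length and sagittal balance (2.2), not comorbidity.

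Nor do the documents show how the literature rates were collected, so it cannot be said how much any shortfall would flatter the comparison.

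**Conclusion.** The point holds for events that have both a disease and a possible surgical cause, or that are wrongly put down to disease. For these, sections 8.2.1 and 8.2.2 give opposite instructions without precedence. The literal exclusion removes events that the primary safety outcome is defined to include, before any record exists for others to review.

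Any loss lowers the absolute rate. Its size cannot be derived from the documents, and it is zero if every site follows the inclusive rule. The figures above show only how the rate would respond to assumed losses.

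For objective 5, at most the capture of adjacent segment disease may be affected. Section 2.3 describes it as degenerative disease, so a site could class it as disease, and no dedicated CRF item for it is listed in 7.3. This is a possibility, not a demonstrated loss.

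**What to change.** 1. In 8.2.1 and 8.2.2, limit the exclusion to events that cannot be related to the procedure or to MagnetOs. State that any event possibly related to either is recorded even if a previous or unknown disease contributed. Wherever the two rules meet, the inclusive rule then applies.
2. For SAEs, record all of them, with separate fields for relatedness to the procedure and to the product, reviewed by the principal investigator. Derive the primary safety outcome as the procedure-related subset. The present include sentence in 8.2.2 must be reworded to match.

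Full recording of unrelated non-serious AEs is not needed.

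The cost is protocol wording, two CRF fields and some additional SAE forms from 100 patients over two years. Because 8.2.2 passes all reported SAEs to the ethics committee, those forms also bring some extra reports. The resulting rate may be less favourable, but its causality judgements can be reviewed.
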